# **Trial Summary**

| Name and Designation   |
|--|
| Chief Investigator (CI): [name], Consultant Burn Surgeon, Royal |
| Victoria Infirmary, Newcastle upon Tyne  |
| Co-investigator: [name], Clinical Psychologist, Royal Victoria    |
| Infirmary, Newcastle upon Tyne   |
| Research Team Lead: [name]  |
| Freeman Hospital, Newcastle upon Tyne  |
| Sponsor: The Newcastle upon Tyne Hospitals NHS Foundation Trust                |
|  |

| Trial Title          | A feasibility study assessing combined pulsed dye and fractional CO 2 laser |  |  |
|----------------------|--|--|--|
|                      | on burn scar outcomes versus standard care   |  |  |
| short title          | CLIPSO (Combined Laser Improves Scar Outcome)  |  |  |
| Clinical Phase       | N.A.   |  |  |
| Trial Design         | Randomized controlled single, blinded study  |  |  |
| Trial Participants   | Adults with hypertrophic burn scars  |  |  |
| Sample Size          | 10 to each treatment arm   |  |  |
| Intervention         | Combination pulsed dye and fractional CO 2 laser versus standard care       |  |  |
| Follow up duration   | 8 months   |  |  |
| Planned Trial Period | 24 months  |  |  |
| Objectives           |  |  |  |
| Primary              | To determine if combined pulsed dye and fractional CO 2 laser treatment     |  |  |
|                      | versus fractional CO 2 laser alone or standard scar therapy improves        |  |  |
|                      | patient and observer reported scar appearance.   |  |  |
| Secondary            | To determine if combined laser treatment versus AFCO 2 L alone              |  |  |
|                      | standard scar therapy on burn scars improves patient reported symptoms                 |  |  |
|                      | of itch and psychological sequelae.  |  |  |
|                      |  |  |  |

# Abbreviations

| AE                  | Adverse Event  |
|---------------------|--|
| AFCO 2 L | Ablative fractional carbon dioxide laser               |
| AR                  | Adverse Reaction                                       |
| BBSIP               | Brisbane Burn Scar Impact Profile                      |
| CI                  | Chief Investigator                                     |
| GCP                 | Good Clinical Practice                                 |
| HRA                 | Health Research Authority                              |
| HT                  | Hypertrophic   |
| ICF                 | Informed Consent Form                                  |
| IRAS                | Integrated Research Application System                 |
| MSS                 | Manchester Scar Scale                                  |
| NRBC                | Northern Regional Burns Centre                         |
| NuTH                | The Newcastle upon Tyne Hospitals NHS Foundation Trust |
| PDL                 | Pulsed dye laser                                       |
| PIS                 | Patient Information Sheet                              |
| POSAS               | Patient observer scar assessment scale                 |
| PPE                 | Personal protective equipment                          |
| R&D                 | Research and Development                               |
| REC                 | Research Ethics Committee                              |
| SAE                 | Serious Adverse Event                                  |
| SAR                 | Serious Adverse Reaction                               |
| TBSA                | Total body surface area                                |
| VSS                 | Vancouver Scar Scale                                   |

# 1. Trial Summary

Hypertrophic (HT) scars following burn injury have an incidence ranging from 30-70% in reviewed data. These scars are red, lumpy and firm and have the potential to severity affect daily quality of life, causing itch, dryness, pain and restriction of joint movement during activities of daily living. Fundamentally, these scars may have a significant physical and psychological impact during rehabilitation, leading to stigmatization.

Advances in acute burn surgical care now means that more people survive major burn injuries, equating to more patients with HT burn scars. However, the optimum treatment for HT scar treatment remains to be elucidated. Different treatment modalities are available for scar treatment, including silicone, corticosteroid injection and compression. Laser therapy is a relatively new modality for the treatment of HT burn scars and is used in burn centres Worldwide for this capacity.

Two lasers show promise in the treatment of HT scars: the 595nm pulsed dye laser (PDL) and the 10,600nm ablative fractional carbon dioxide laser (AFCO2L). Both lasers have been used individually and in combination for burn scar treatment. PDL is typically used to help reduce erythema and pruritus, while AFCO2L is used to improve scar texture and thickness.

The aim of this study is to combine both laser treatments to investigate if the early use of combination laser treatment helps improve HT burn scar appearance (colour/texture) and associated symptoms including itch. Whilst these lasers have been used in combination before for the treatment of burn scars, this study is unique in that we will assess patient reported outcome measures, together with observer scar assessment tools.

A 10,600nm AFCO2L (Lumenis) and a 595nm PDL (Candela) are the device to be used in this study. These lasers are both in routine use in the host institution and Worldwide for the treatment of scars and vascular lesions. They deliver precise high energy in short pulses to thickened scars and have a good record for safety and

outcomes. The Northern Regional Burn Centre has extensive experience in the use and delivery of both lasers and all health professionals involved have received the appropriate safety training.

Participants will be divided into three groups: control, AFCO2L only and combined PDL and AFCO2L treatment. Both laser groups will receive 3 treatments 6 weeks apart. Outcome measures will be conducted before laser treatment, 6 weeks after the last treatment of laser and 3 months post laser treatment. This feasibility study will serve to inform a larger multi-centre RCT in terms of study power, outcome measure frequency and whether treatment streams can be refined.

## 2. Background

Both PDL and AFCO2L are established to play a role in the treatment of post-burn HT scars. Literature review identified 3 clinical trials surrounding the clinical response to AFCO2L alone and 4 papers reporting the combined use of AFCO2L and PDL for scar treatment.

 $Qu^2$  reported on 10 participants treated with AFCO2L for post-burn HT scars. This uncontrolled prospective trial demonstrated measurable improvements on both Vancouver Scar Scale (VSS) and Patient Observer Scar Assessment Scale (POSAS) scar assessment at final follow-up (2 months after final treatment). Biopsy results showed a statistically significant reduction in mRNA expression of both TGF- $\beta$ 2 and 3 after treatment. Furthermore, bFGF mRNA expression was significantly decreased in the acute phase after treatment, whereas MMP-1 expression was increased.

The prospective case series of Waibel aimed to highlight the potential augmentation of AFCO2L with the application of corticosteroid ointment immediately post-operatively. Of the parameters measured, texture received the highest improvement score, while dyschromia displayed the least. The overall improvement score was 2.73, which according to the authors, correlates to an improvement between 50-75% from baseline.

Ozog conducted an uncontrolled, prospective study of 10 participants demonstrating a statistically significant improvement in VSS and POSAS at 2 months post treatment following AFCO2L. Furthermore, a statistically significant decrease in type I collagen and a statistically significant increase in type III collagen was seen in the posttreatment biopsy specimens. Blinded analysis of post-treatment slides showed a statistically significant improvement in collagen structure post-treatment, with a change towards normal dermal framework.

Zuccaro retrospectively reported on the use of combined PDL and AFCO2L in the treatment of paediatric burn scars. This reported an improvement in VSS score following treatment but was uncontrolled with no further outcome measures.

Ouyang conducted a controlled prospective trial comparing PDL alone with combined PDL and AFCO2L for the treatment of HT scars. This study used VSS as the sole outcome measure, finding an improvement in scar thickness, redness and pliability, both with single and combined laser treatment.

Lei combined PDL and AFCO2L for the treatment of paediatric burn scars and reported the retrospetive uncontrolled data. Using unblinded POSAS assessments, significant improvements were found, but with no further outcome measures performed.

The reported biochemical and photomechanical processes associated with the clinical efficacy of AFCO2L have improved our understanding of this treatment modality. However, there is a paucity of high-quality data regarding the combined use of PDL and AFCO2L, both in terms of patient-reported outcome measures (PROMs), blinded observer scar assessment and skin biology. With robust and appropriate PROMs, this study hopes to yield data that informs our understanding of scar biology and remodelling in response to laser therapy and the clinical impact for patients.

# 3. Project Aim, Objectives & Hypothesis

## 3.1 Aim

To investigate if the early use of combination laser treatment helps minimise scar, improves patient satisfaction with scar appearance and associated symptoms versus single AFCO2L treatment or standard care alone.

## 3.2 Objectives

- To determine the effect of combined PDL and AFCO2L treatment on the subjective and objective clinical appearance of burn scars versus AFCO2L alone or standard scar therapy.
- To determine if combined laser treatment versus AFCO2L alone or standard scar therapy on burn scars improves patient reported symptoms of itch and psychological sequelae.

## 3.3 Hypothesis

Combined PDL and AFCO2L treatment improves scar redness and pliability, reduces patient-reported scar-related distress and improves scar-related symptoms.

# 4. Study design

## 4.1 Type of research

Prospective, randomised, single-centre, single blinded (observer) controlled trial of combination PDL and AFCO2L therapy to immature burn scars in adult patients with a burn scar between 1% and 5% total body surface area (TBSA), which meet inclusion criteria. This is a feasibility study to inform the development of a larger multi-centre RCT. In view of this, 10 patients will be recruited to each treatment arm and subsequent data analysis will reflect on wider RCT design and power.

## 4.2 Inclusion Criteria

- Participants > 18 years of age
- Hypertrophic burn scar ≥1% and 5% TBSA
- Scars which would ordinarily be managed by pressure garments and laser intervention
- All patients to be less than 3 months from discharge at point of recruitment.

## 4.3 Exclusion Criteria

- Participants < 18 years of age
- Pregnant or lactating females
- Facial scars
- Keloid scars
- Large (>5% TBSA) symptomatic hypertrophic scars not amenable to topical anaesthetic laser treatment
- Participants requiring general anaesthesia or block anaesthesia for laser treatment
- Scar of non-burn aetiology
- Previous topical or intralesional steroid treatment to study scar
- Mature (pale) scars more than 18 months following injury
- Inability to give informed consent
- Systemic glucocorticoid use
- Fitzpatrick skin types 4 6

## 5. Methods

All adult patients treated at the Royal Victoria Infirmary Northern Regional Burn Centre will be screened for admission. Those patients who meet the selection criteria will be informed about the study and asked to participate at their six-week clinic appointment.

Each patient will be randomised to one of three groups: COMBINED LASER (CL), SINGLE LASER (SL) or CONTROL (C) group. A single hypertrophic scar site >1% -5% TBSA is required for each patient. This scar size is deemed appropriate for topical local anaesthesia laser treatment as an outpatient.

[figure not shown]
In the event that the patient has multiple or large areas of hypertrophic scar, study participation will only be offered if laser treatment under topical local anaesthesia is possible and if the study participant consents to this. If the study PI feels this is not feasible, study participation will not be offered and the patient will continue with standard of care as provided by the host unit.

The rationale for this is that it is unethical to treat an area of hypertrophic scar within a large scar burden as standard of care in our host institution would be to treat all areas with AFCO2L if deemed a suitable candidate. Furthermore, previous experience has illustrated that the subjective nature of PROMs makes it difficult for participants to provide meaningful answers if a small area of scar has been treated within a large scar volume; it is not possible to selectively comment on the daily physical/psychological impact of a small treated area if most of a limb/body is scarred.

#### Figure 1. Schematic diagram of the research design and stages

## 5.1 Intervention

All enrolled treatment arm patients (CL and SL groups) will receive laser under topical local anaesthetic due to the discomfort associated with the treatment. This approach is already employed in the host institution, whereby all patients undergoing AFCO2L for small (<5% TBSA) areas are treated with topical LMX4 (4% lidocaine) cream for 60 minutes under occlusion prior to laser treatment.

## 1. COMBINED & SINGLE AFCO2 LASER GROUP

In the combination laser group, PDL therapy will always be delivered first using the 595nm VBeam Perfecta (Candela) with the following settings:

10mm spot size (or proportionate to scar size and shape)
0.45 millisecond pulse duration
1.5Hz
5-7 Joule/cm^2 fluence
No overlap
Single pass
Dynamic cooling device 20/30 setting

The energy is selected to produce a degree of purpura/bruising during treatment without skin blanching. The skin response is instantaneous and should be dark purple to black. Whitening in the treatment area suggests over-treatment and is to be avoided. Once the desired response is seen, the entire trial scar is to be treated.

AFCO2L therapy is delivered using the 10,600nm fractional CO2 Ultrapulse laser (Lumenis) with the following settings:

30mJ – 50mJ micropulse energy Rate 300Hz 5% density DeepFX setting No overlap Single pass CLIPSO Feasibility Protocol Version 1.7 8th March 2023; IRAS ID 301064

A cool compress will be applied for 10 minutes following laser completion to dissipate any residual heat. All laser will be administered by the study PI who has laser experience and training.

Following laser delivery, vaseline emollient will be applied topically to all laser sites and dressed with non-adhesive silicone dressing. Patients are advised to remove these at home after 48 hours then apply paraffin emollient twice daily to all treated areas for two weeks. Patients are advised to avoid swimming for two weeks following laser. Following removal of dressings, all sites will be treated with standard scar treatments (pressure garment treatment, silicone, massage and moisturiser) by the scar therapy team.

The laser treatment will be delivered to intervention sites three times at six-week intervals. The time points for intervention have been determined based on a data from previous published research, as well as the clinical expertise of the PI who has conducted laser treatments and clinically evaluated individual response to therapy.

All laser settings will be recorded for each visit. At subsequent visits, participants will be asked to report any adverse effects of the treatment and laser will be delivered using the previous settings.

All participants in the treatments and control arms will receive standard scar therapy, which may include scar moisturisation, massage, silicone and pressure garments dependent on scar quality. Standard scar care will be delivered by a senior scar therapist. To avoid patient inconvenience and excess appointments, study visits will be coordinated with scar therapy team to occur at the same time.

# 5.2 Measures taken to minimise/avoid bias, including randomisation and blinding

Patients cannot be blinded to intervention in this study due to the nature of laser. In addition, sham treatment is not possible as study laser treatment results in localised heat, discomfort during laser delivery, bruising and a temporary grid of microscopic holes secondary to microthermal channel creation within the scar. These will be visible CLIPSO Feasibility Protocol Version 1.7 8th March 2023; IRAS ID 301064 13

to patients following dressing removal. The investigator conducting the outcome measures will be aware of the scar enrolled in the study but will be blinded as to whether it is in the control or treatment arm. Any indication of laser treatment will have settled prior to blinded scar evaluation at four and eight months following intervention (timepoints for independent objective scar evaluation). The study incorporates an interval of four weeks between the last laser session and blinded outcome measures, to ensure any sequelae of treatment have settled and negate observer bias.

# 5.3 Maintenance of any blinding records or randomisation codes and procedures for breaking codes

The Sealed Envelope online software (www.sealedenvelope.com) will be used to randomly allocate study participants to combined laser (CL), single laser (SL) or control (C) groups. The PI will select the scar and the anatomical location of the scar, and the site name (CONTROL, COMBINED LASER or SINGLE LASER) will be recorded immediately on a spread sheet. The area will be marked and photographed prior to treatment and following patient consent for medical photography images. There is no foreseen scenario whereby the laser site or the control site will be required to change. As this is a single blinded study, participants will know which treatment arm they are in negating the necessity to break blinding.

## 5.4 Data collection

# 1. COMBINED LASER (CL) group

| Study visit 1                 | Study visit 2                 | Study visit 3                 | Study visit 4 | Study visit 5 |
|-------------------------------|-------------------------------|-------------------------------|---------------|---------------|
| 3/12 post burn                | Study week 6                  | Study week 12                 | Study month 4 | Study month 8 |
| Study week 0                  |                               |                               |               |               |
| 1 st laser session | 2 nd laser session | 3 rd laser session |               |               |
| Ongoing scar therapy regime   |                               |                               |               |               |
| MSS                           |                               |                               | MSS           | MSS           |
| POSAS                         |                               |                               | POSAS         | POSAS         |
| BBSIP                         |                               |                               | BBSIP         | BBSIP         |
| Photographs                   | Photographs                   | Photographs                   | Photographs   | Photographs   |
| Colorimeter                   |                               |                               |               | Colorimeter   |

# 2. SINGLE LASER (SL) group

| Study visit 1                 | Study visit 2                 | Study visit 3                 | Study visit 4 | Study visit 5 |
|-------------------------------|-------------------------------|-------------------------------|---------------|---------------|
| 3/12 post burn                | Study week 6                  | Study week 12                 | Study month 4 | Study month 8 |
| Study week 0                  |                               |                               |               |               |
| 1 st laser session | 2 nd laser session | 3 rd laser session |               |               |
| Ongoing scar therapy regime   |                               |                               |               |               |
| MSS                           |                               |                               | MSS           | MSS           |
| POSAS                         |                               |                               | POSAS         | POSAS         |
| BBSIP                         |                               |                               | BBSIP         | BBSIP         |
| Photographs                   | Photographs                   | Photographs                   | Photographs   | Photographs   |
| Colorimeter                   |                               |                               |               | Colorimeter   |

# 3. CONTROL (C) group

| Study visit 1  | Study visit 4         | Study visit 5 |
|----------------|-----------------------|---------------|
| 3/12 post burn | Study month 4         | Study month 8 |
| Study week 0   |                       |               |
| Ongo           | oing scar therapy reg | gime          |
| MSS            | MSS                   | MSS           |
| POSAS          | POSAS                 | POSAS         |
| BBSIP          | BBSIP                 | BBSIP         |
| Photographs    | Photographs           | Photographs   |
| Colorimeter    |                       | Colorimeter   |

#### 5.5 Outcome Measures

The **Patient Observer Scar Assessment Scale (POSAS)** is a standardized measure whereby the patient rates all aspects of the appearance of a scar with the addition of questions regarding pain, itch and overall impression of the scar. The POSAS is reported to be reliable and valid scales that measure single-construct scar quality, as demonstrated by Rasch model analysis.

The **Manchester Scar Scale** objectively assess scar appearance will be used to assess the effectiveness of treatment of HTS. This assesses colour, contour, distortion, texture and sheen, and has been validated to show a strong correlation with micro and macroscopic features within a scar.

All patients will have standardized **digital clinical photographs** taken at all appointments. These will be performed with a digital camera on a grey/white background and will be deidentified. All photographs will record the following ID card including randomized number, study visit day, date and time of image capture.

**The Brisbane Burn Scar Impact Profile (BBSIP) assessment questionnaire** will be used to assess health-related quality of life in people with burn scars across three key domains: scar appearance (size, colour, contour), scar symptoms (painful, tight, itchy) and psychosocial impact (feeling self-conscious, bothered by scar). This has been extensively validated as an internationally applicable PROM. As this

CLIPSO Feasibility Protocol Version 1.7 8th March 2023; IRAS ID 301064

questionnaire contains questions about symptoms of depression and anxiety all participants who report concerns of depression and anxiety will be referred to the burns clinical psychologist within 24 hours.

**Demographic information and standard clinical care** will be recorded into an electronic database from information provided in electronic medical records. Variables recorded including age, gender, TBSA, length of stay, surgical intervention, data of pressure garment application, date of pressure garment removal, scar management interventions. This data will be accessed by the PI and nominated research team members. Data will be recorded alongside the participant ID for each patient in a pseudo-anonymised form.

**Colorimetry** using a digital colorimeter will provide data on scar erythema and pigmentation. Both parameters will be measured at enrolment and study conclusion to assess whether combination laser alters scar redness and pigmentation versus standard care. Measurements are taken in triplicate from a region of interest in the study scar, allocated by the PI. Control colorimeter measurements are taken from the contralateral area if It is scar-free. If there is no contralateral area free of scar, an alternate site of unscarred skin may be used and documented.

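### The unblinded PI chooses the study scar and the colorimeter region, and the text does not require either to be fixed before randomisation or the same region to be re-measured at month 8

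*Protocol*

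**What the plan says.** Four parts of the protocol bear on this.

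- **Who knows the arm.** Section 5.1, on the laser groups: "All laser will be administered by the study PI who has laser experience and training".
- **Who chooses the scar.** Section 5.3 first describes random allocation by the online service, and then says: "The PI will select the scar and the anatomical location of the scar". In the same sentence, "the site name (CONTROL, COMBINED LASER or SINGLE LASER) will be recorded immediately on a spread sheet". It continues: "The area will be marked and photographed prior to treatment".
- **Who chooses the colorimeter region, and when it is read.** Section 5.5: "Measurements are taken in triplicate from a region of interest in the study scar, allocated by the PI". On timing: "Both parameters will be measured at enrolment and study conclusion". The schedules in section 5.4 place these readings at visit 1 (week 0) and visit 5 (month 8) in all three arms. Section 1 gives a more general timing: "Outcome measures will be conducted before laser treatment".
- **Who is blinded.** Section 5.2: "The investigator conducting the outcome measures will be aware of the scar enrolled in the study but will be blinded". It names months four and eight as the blinded evaluations.

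Section 5 requires one scar site per patient. It also lets patients with several or extensive scars enter if the treatment is feasible under topical anaesthetic and they agree.

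**The concern.** Blinding the person who takes a reading protects it only if the place of the reading was settled without knowledge of the arm. Here the person who settles the place is the one who delivers the laser. Colour can differ between scars and from one part of a scar to another. If the region is placed, or placed again at month 8, by someone who knows the arm, the laser and control arms may differ in colour for a reason unrelated to treatment.

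Colorimetry deserves this protection more than most outcomes here. MSS, POSAS and BBSIP are ratings, and section 5.2 accepts that patients cannot be blinded. The instrument reading should be the measure least open to expectation, and redness is named in the hypothesis in section 3.3. The study is meant to inform the design and power of a larger trial, so a distorted colour effect would carry forward. Analysis cannot repair it afterwards, because a region chosen with knowledge of the arm cannot be chosen again.

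**Working it through.** **Step 1: what is fixed, and relative to what.**

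| Item | Decided by | Timing stated | Placed before randomisation? |
|---|---|---|---|
| Study scar | PI (5.3) | none; the sentence follows the one on allocation | not stated |
| Marking and photograph of the area | not stated | before treatment (5.3) | not stated |
| Colorimeter region | PI (5.5) | none | not stated |
| Baseline colorimetry | not stated | enrolment (5.5), week 0 (5.4) | not stated |
| Month 8 region | not stated | none; no rule to return to the same place | not applicable |

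Enrolment and week 0 are not themselves placed before or after randomisation. Following the text as written therefore allows the scar and the region to be chosen with the arm known.

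**Step 2: how large could it be?** The protocol gives no figure for this, so there is none to reproduce. The only input it supplies is 10 participants per arm (section 5.6). The rest of the illustration is assumed:

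- no true effect;
- between-patient SD of the colour change set to 1;
- within-scar (between-region) SD of *r*, in the same units;
- laser-arm region the most favourable of *k* candidates, control-arm region random;
- two-sided two-sample t-test at 0.05, with 40,000 simulated trials per setting.

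The expected best of *k* standard normal values, m(k), is 0.56 for k = 2, 0.85 for k = 3 and 1.16 for k = 5. The spurious difference is r × m(k). Divided by the control-arm SD, √(1 + r²), it is in outcome SDs. For example, with r = 0.5 and k = 3: 0.5 × 0.85 = 0.42, and 0.42 / √1.25 = 0.38.

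| r | k | Shift, outcome SDs | False-positive rate |
|---|---|---|---|
| 0.25 | 2 | 0.14 | 6.0% |
| 0.25 | 3 | 0.21 | 7.3% |
| 0.25 | 5 | 0.28 | 9.3% |
| 0.5 | 2 | 0.25 | 8.0% |
| 0.5 | 3 | 0.38 | 12.9% |
| 0.5 | 5 | 0.52 | 20.5% |
| 1.0 | 2 | 0.40 | 14.1% |
| 1.0 | 3 | 0.60 | 27.0% |
| 1.0 | 5 | 0.82 | 46.6% |

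**Step 3: how to read the table.** It assumes perfect selection in one arm and none in the other, so for a given r and k it is close to a worst case. It fits best a fresh choice of region at month 8. If the region is fixed at baseline, the chooser would have to predict which part of the scar will change most, and the shift would be smaller.

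**The case against.** The strongest reply is that the protocol already closes most of the route. A blinded investigator conducts the outcome measures at months four and eight. Each patient contributes a single scar site, and the area is marked and photographed before treatment. Section 5.5 speaks of one region, in the singular, which can be read as the same region at both times. Figure 1, the schematic of the design stages, is not available in the text reviewed and may show baseline before randomisation. The primary objective concerns patient- and observer-reported appearance and does not name colorimetry, and this is a 30-patient feasibility study.

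Much of this narrows the concern, but it does not close it. Blinding of the assessor does not extend to the choice of region. Marking before treatment is not marking before allocation. The single-site rule leaves a choice in patients with several scars. A figure could settle the order of steps, but would be unlikely to settle who places the region or whether it is revisited.

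Three stronger readings are tempting and are not supported:

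- *Baseline is tied only to the start of laser, and so follows randomisation.* Section 5.5 ties colorimetry to enrolment and section 5.4 ties all baselines to week 0. The order is unstated, not wrong.
- *Patients already know their arm when they give baseline POSAS and BBSIP answers.* Baseline shares visit 1 with the first laser session, so this is possible, but nothing says when patients learn their allocation.
- *The PI takes the colorimeter readings.* Section 5.5 says only that the PI allocates the region.

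**Conclusion.** The point holds as an opening for bias, not as a demonstrated bias. An unblinded person chooses the scar and the region for the only instrument-read outcome. The text neither requires those choices to precede allocation nor requires the same region to be used at month 8.

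Its size cannot be stated. Under the assumptions above, the false-positive rate moves little when regions within a scar are similar (6.0% to 9.3% at r = 0.25) and a great deal when they differ as much as patients do (14.1% to 46.6% at r = 1). The documents do not say which is closer.

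A reader might set the raw values 0.56 and 0.85 beside the 95% interval half-width for 10 per arm, 2.101 × √(2/10) = 0.94, and infer that selection could pass for a real effect. That comparison is not valid: the first two are in between-region SDs and the last is in outcome SDs. Even at r = 1 the shifts for k = 2 and 3 are 0.40 and 0.60 outcome SDs, below 0.94.

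The change should be made, because the stated procedure leaves an avoidable route for bias and a less biased one is available for little effort. It does not threaten the study as a whole.

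**What to change.** In sections 5.3 and 5.5, state the order of steps:

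1. The PI selects the study scar and marks the colorimeter region on the baseline photograph.
2. Only then is the allocation requested from the online service.
3. At month 8, the assessor already blinded under section 5.2 relocates that mapped region from the photograph and re-measures it.

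Where scheduling allows, also complete baseline colorimetry, MSS, POSAS and BBSIP before the allocation is requested. If Figure 1 already shows this order, the text should say the same.

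The cost is a few sentences, with no extra staff or measurements. The downside is that allocation waits for these steps. Baseline and the first laser session share visit 1, so completing all baseline measures first may mean holding a laser slot for a patient who is then allocated to control, or separating the two appointments. Fixing only the scar and the mapped region before allocation is the lighter option and removes the main route.
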